## **STATISTICAL ANALYSIS PLAN AMENDMENT RATIONALE FOR VERSION 3**

- Change to Section 4.1.2.1 (Modified Intent to Treat [mITT] Population): Update the mITT Population definition to clarify it will not be used for histologic remission analysis.
- Change to Section 4.4 (Efficacy Analysis): Update to methodology for handling for treatment discontinuation intercurrent events to set to missing and remove single imputation of worst observation carried forward.
- Change to section 4.4.5 (Supplementary Analyses): Added in sensitivity analysis for key secondary endpoints calculated as applicable.
- Change to Section 4.1.1.2 (OLI Histology Evaluable Population) and Section 4.1.2.3 (Histology Evaluable Population) were made to clarify main analysis and sensitivity analysis populations.

Additional minor changes have been made to improve clarity and consistency.

## GLOSSARY OF ABBREVIATIONS

AE	adverse event
CMH	Cochran–Mantel–Haenszel
CCOD	clinical cutoff date
CS	Corticosteroids
e-CRF	electronic Case Report Form
EQ-5D	EuroQoL Five-Dimension Questionnaire
Etro	Etolizumab
ES	endoscopic subscore
HRQoL	health-related quality of life
IBDQ	Inflammatory Bowel Disease Questionnaire
ICE	intercurrent event
IS	immunosuppressants
IxRS	interactive voice/web based response system
LoPO	list of planned outputs
MCS	Mayo Clinic Score
mITT	modified intent-to-treat
mMCS	modified Mayo Clinic Score
NHI	Nancy Histology Index
OLE	open-label extension
OLI	open-label induction
PBO	Placebo
PGA	Physician’s Global Assessment
PK	Pharmacokinetic
pMCS	partial Mayo Clinic Score
QOL	quality of life
RB	rectal bleeding
SAP	Statistical Analysis Plan
SF	stool frequency
SM	safety monitoring
TNF	tumor necrosis factor
UC	ulcerative colitis
UC-PRO/SS	Ulcerative Colitis Patient-Reported Outcome Signs and Symptoms

## 1. BACKGROUND

This Statistical Analysis Plan (SAP) describes the analyses to be performed for Study GA29102. Study GA29102 is part of a large Phase III development program for etrolizumab. Details which are common to Studies GA28950, GA29102, GA28948, GA28949, and GA29103 are described in the project SAP.

[figure not shown]
Study GA29102 is made up of two phases: the Induction Phase and the Maintenance Phase. The Induction Phase is made up of a single open-label etrolizumab arm; therefore, no statistical comparisons will be made for the Induction Phase. Induction Phase data will be summarized descriptively and pre-specified in the list of planned outputs (LoPO). Statistical analyses will only be conducted for the Maintenance Phase of the study.

The Induction and Maintenance Phases will be reported once data from the Week 62 treatment period have been collected in the database and data have been cleaned and verified; this will be referred to as the primary analysis.

## 2. STUDY DESIGN

This is a multicenter, Phase III, double-blind, placebo-controlled study evaluating the safety, efficacy, and tolerability of etrolizumab in patients who achieved a clinical response to etrolizumab treatment after 10 weeks. The population is made up of moderate to severe ulcerative colitis (UC) patients who are naive to tumor necrosis factor (TNF) inhibitors (see Figure 1).

**Figure 1 Study Schema**

6-MP=6-mercaptopurine; AZA=azathioprine; d=day; CS=corticosteroid; MTX=methotrexate; OLE=open-label extension; OLE-SM=open-label extension and safety monitoring; Q4W=every 4 weeks; QOD=every other day; SC=subcutaneous; SM=safety monitoring; TNF=tumor necrosis factor; UC=ulcerative colitis; wk=week.

a Stable budesonide at ≤9 mg/day. Taper from Week 10 to QOD for 2 weeks and then discontinue.

**Etrolizumab—F. Hoffmann-La Roche Ltd**  
7/Statistical Analysis Plan GA29102

**Clinical Study Report: etrolizumab - F. Hoffmann-La Roche Ltd**  
Protocol GA29102 Report Number 1099518

Following participation in this study, patients may be eligible to participate in an open-label extension and safety monitoring (OLE-SM) Study GA28951, which consists of two parts: Part 1 (designated OLE [open-label extension]) and Part 2 (designated SM [safety monitoring]).

## **2.1 PROTOCOL SYNOPSIS**

The Protocol Synopsis is in [Appendix 1](#). For additional details, see the Schedule of Assessments in [Appendix 2](#).

## **2.2 OUTCOME MEASURES**

Baseline throughout this document is defined as the last available assessment prior to first receipt of study drug in the Induction Phase. The efficacy outcome measures listed below deviate from the current Study GA29102 Protocol Version 7. The current protocol includes change from baseline in stool frequency (SF) and rectal bleeding (RB) at Week 6 as secondary outcomes measures, and endoscopic remission at Week 10, histologic disease activity change from baseline to Week 10, improvement in the endoscopic mucosa at Week 10, and change in health utilities, as assessed by the EuroQoL Five-Dimension Questionnaire (EQ-5D) from baseline to Week 10 as exploratory outcome measures. These outcomes measures cannot be analyzed due to no comparator arm at Week 6 or Week 10; therefore, they have been removed from the list below. The safety and pharmacokinetic (PK) measures can be found in the Protocol Synopsis in [Appendix 1](#).

### **2.2.1 Efficacy Outcome Measures**

#### **Primary Outcome Measure**

- Remission at Week 62 among patients with a clinical response at Week 10, as determined by the Mayo Clinic Score (MCS)

#### **Secondary Outcome Measures**

- Clinical remission at Week 62 among patients in clinical remission at Week 10
- Clinical remission at Week 62
- Remission at Week 62 among patients in remission at Week 10
- Improvement in endoscopic appearance of the mucosa at Week 62
- Endoscopic remission at Week 62
- Histologic remission at Week 62
- Corticosteroid-free clinical remission at Week 62 (off corticosteroids [CS] for at least 24 weeks prior to Week 62) in patients who are receiving corticosteroids at baseline
- Corticosteroid-free remission at Week 62 (off corticosteroids for at least 24 weeks prior to Week 62) in patients who are receiving corticosteroids at baseline
- Change from baseline to Week 62 in UC bowel movement signs and symptoms as assessed by the Ulcerative Colitis Patient-Reported Outcome Signs and Symptoms (UC-PRO/SS) measure

**Etrolizumab—F. Hoffmann-La Roche Ltd**  
8/Statistical Analysis Plan GA29102

- Change from baseline to Week 62 in UC functional symptoms as assessed by the UC-PRO/SS measure
- Change from baseline to Week 62 in patients' health-related quality of life (HRQoL) as assessed by the overall score of the Inflammatory Bowel Disease Questionnaire (IBDQ)

### **Exploratory Efficacy Outcome Measures**

- Clinical response at Week 62 among patients with a clinical response at Week 10
- Remission at Week 62 among patients in clinical remission at Week 10
- Corticosteroid-free clinical remission at Week 62 (off corticosteroids for at least 12 weeks prior to Week 62) in patients who are receiving corticosteroids at baseline
- Histologic disease activity change from baseline to Week 62
- Improvement in histologic and/or endoscopic disease activity
- Change in health utilities, as assessed by the EQ-5D, from baseline to Week 62
- Frequency and duration of hospitalizations from Week 10 to Week 62
- Response, remission and corticosteroid-free endpoints as determined by the modified Mayo Clinic Score (mMCS)

## **2.3 DETERMINATION OF SAMPLE SIZE**

### **2.3.1 Sample Size**

The study sample size was selected so that sufficient patients are enrolled to evaluate the primary endpoints in the Maintenance Phase. Approximately 350 patients will be enrolled in the open-label induction (OLI) arm and, under the assumption of 60% of patients being clinical responders at Week 10, approximately 210 patients (previously treated with etrolizumab in the OLI phase) will be randomized into the Maintenance Phase.

The primary endpoint is Week 62 remission among patients in clinical response at Week 10. A sample size of 105 patients per arm in the Maintenance Phase will provide >90% power to detect a 25% absolute difference in remission rates between the etrolizumab and placebo Maintenance arms for a chi-squared test at the 5% significance level, under the assumption of a placebo true remission rate 30%–45%.

## **2.4 ANALYSIS TIMING**

The primary analysis for the Induction and Maintenance Phases will be conducted once the last patient has completed their Week 62 treatment period or has discontinued from study treatment. The date associated with this visit will be termed the clinical cutoff date (CCOD) for the primary analysis, and data in the study database to the CCOD will be cleaned and verified. Sponsor personnel will be unblinded to treatment assignment to perform the primary analysis. Patients and study site personnel will remain blinded to individual Maintenance Phase treatment assignment until after the study is completed

(after all patients have either completed the safety follow-up periods or discontinued early from the study) and the database is locked.

Additional analyses will be conducted once all patients have completed 12 weeks safety follow-up and the database has been locked. These analyses will report all adverse events (AEs) including the data collected in the 12-week safety follow-up period.

### **3. STUDY CONDUCT**

#### **3.1 RANDOMIZATION**

Details of the randomization process are included in the project SAP, Section 3.1. The statistical analyses will be conducted using the stratification factors entered into the interactive voice/web based response system (IxRS) system at randomization. Sensitivity analysis of the primary endpoints using data collected in the clinical database will be conducted as required, if the database does not match IxRS due to incorrect stratification data being collected in IxRS at randomization. Due to low or zero counts in any one stratum, the stratification factors may need to be combined or removed in the primary analysis to ensure the Cochran–Mantel–Haenszel (CMH) test is not invalidated. This approach has been applied to the Maintenance Phase as described in Section 3.1.1, however further combining or removal may be required to ensure the analysis is not invalidated due to zero counts.

##### **3.1.1 Maintenance Phase**

Patients who achieved a clinical response at Week 10 and did not receive (permitted/non-permitted) rescue therapy during the Induction Phase were eligible to be randomized into the Maintenance Phase following enrolment into the Induction Phase. Patients were randomized to etrolizumab or placebo using a 1:1 ratio and a permuted blocks stratified randomization (dynamically generated). Patients were stratified using the following stratification factors:

- Concomitant treatment with CS at baseline (yes/no)
- Concomitant treatment with immunosuppressants (IS) after Week 10 (yes/no)
- Disease activity at screening MCS  $\leq 9$ /MCS  $\geq 10$ )
- Remission criteria at week 10 (No remission/ remission including Physician's Global Assessment (PGA) subscore /remission not including PGA subscore)

The Sponsor conducted a blinded review of the study data and concluded zero or low counts are likely to occur within multiple stratum when using the stratification factor 'Remission Criteria at Week 10'. This scenario would invalidate the CMH test, the Sponsor proposes not to fit 'Remission Criteria at Week 10' as a term within the analysis models.

All maintenance analysis will, therefore, be adjusted for using the following three stratification factors:

- Disease activity at screening (MCS  $\leq$ 9/MCS  $\geq$ 10)
- Concomitant treatment with CS at baseline (yes/no)
- Concomitant treatment with IS after Week 10 (yes/no)

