6.4.1 Primary Efficacy Endpoint

The primary endpoint for the Maintenance Phase is Week 62 remission among patients *with a clinical response at Week 10. Patients who are randomized into the Maintenance Phase (i.e., clinical responders at Week 10) will be evaluated.* The difference in remission rates between the etrolizumab and placebo arms will be compared using the Cochran-Mantel-Haenszel test statistic stratified by concomitant treatment with corticosteroids at baseline (yes/no), concomitant treatment with immunosuppressants after Week 10 (yes/no), and baseline disease activity (MCS ≤ 9 , MCS ≥ 10). The absolute difference in remission rates and 95% CIs for the point estimate will be provided.

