6.4.2 Secondary Efficacy Endpoints

The secondary efficacy endpoints for the Maintenance Phase are as follows:

- Proportion of patients *in* clinical remission at Week 62 among patients in clinical remission at Week 10
- Proportion of patients in clinical remission at Week 62
- *Proportion of patients in remission at Week 62 among patients in remission at Week 10*
- Proportion of patients with improvement in endoscopic appearance of the mucosa at Week 62
- Proportion of patients in endoscopic remission at Week 62
- Proportion of patients in histologic remission at Week 62
- *Change from baseline in rectal bleed subscore at Week 6*
- *Change from baseline in stool frequency subscore at Week 6*
- Proportion of patients in corticosteroid-free remission at Week 62 (off corticosteroids for at least 24 weeks prior to Week 62) in patients who were receiving corticosteroids at baseline

- Proportion of patients in corticosteroid-free clinical remission at Week 62 (off corticosteroids for at least 24 weeks prior to Week 62) in patients who were receiving corticosteroids at baseline
- Change from baseline to Week 62 in UC bowel movement signs and symptoms as assessed by the UC-PRO/SS measure
- Change from baseline to Week 62 in UC abdominal symptoms as assessed by the UC-PRO/SS measure
- Change from baseline to Week 62 in health-related QOL, as assessed by the overall IBDQ score.

All the responder/remitter type secondary endpoints will be analyzed in the same fashion as the primary endpoint. The continuous secondary endpoints will be analyzed using an analysis of covariance (ANCOVA) model with Week 10 remission status, concomitant treatment with corticosteroids, concomitant treatment with immunosuppressants, baseline disease activity ($MCS \leq 9$, $MCS \geq 10$) as stratification variables, and the baseline value of the studied measure as a covariate.

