#### **4.1.2 Maintenance Phase**

##### **4.1.2.1 Modified Intent-to-Treat (mITT) Population**

Efficacy analyses for the Maintenance Phase will be performed using a modified intent-to-treat (mITT) analysis population (with the exception of histologic remission). This analysis population will include patients randomized in the Maintenance Phase who received at least one dose of maintenance study drug. Patients will be grouped according to the treatment assigned at maintenance randomization.

To allow consistency across the program the mITT population is being used. This differs to terminology in the Protocol Version 7, Section 6.4, which uses intent-to-treat population.

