#### 4.4.2.3 UC-PRO

The UC-PRO questionnaire is collected in the e-diary and completed by patients for at least 9–12 consecutive days prior to a study visit as per the Schedule of Assessments in the protocol. The UC-PRO is being reported in three domains; two domains are key endpoints and reported as UC-PRO Signs and Symptoms. This data was not collected in the GA29103 study.

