#### **Change from Baseline at Week X**

$$= \text{Week X UC-PRO/SS Domain Score} - \text{Baseline UC-PRO/SS Domain Score}$$

A MMRM (Mixed Model Repeated Measures) analysis will be performed to assess the change from baseline in UC-PRO domains at Week X and will include the fixed categorical effects of treatment, visit, study stratification factors, and treatment-by-visit interaction, and the continuous covariates of the baseline continuous UC-PRO domain and baseline UC-PRO domain-by-visit interaction. An unstructured covariance matrix will be used to model the within patient errors within the MMRM.

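### Study SAP 3.1.1 removes Week 10 remission from every Maintenance analysis on a ground that is wrong for the CMH test and irrelevant to the continuous-endpoint models, where it contradicts Protocol 6.4.2

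*SAP*

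**What the plan says.** Protocol 4.2 and study SAP 3.1.1 stratify the Maintenance randomisation by corticosteroid use at baseline, immunosuppressant use after Week 10, screening MCS (9 or below, 10 or above) and Week 10 remission status in three levels.

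Study SAP 3.1.1 reports a blinded data review that expects zero or low counts in several strata once Week 10 remission is used. It concludes: "This scenario would invalidate the CMH test, the Sponsor proposes not to fit" that factor. It then limits every Maintenance analysis to the other three factors.

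The other texts on adjustment are these:

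- Protocol 6.4.1 has the primary CMH test "stratified by concomitant treatment with corticosteroids at baseline (yes/no), concomitant treatment with immunosuppressants after Week 10 (yes/no), and baseline disease activity". Week 10 remission is not in that list. Protocol 6.4.2 treats the responder-type secondary endpoints the same way.
- Protocol 6.4.2 analyses the continuous secondary endpoints with an "analysis of covariance (ANCOVA) model with Week 10 remission status, concomitant treatment with corticosteroids, concomitant treatment with immunosuppressants", baseline disease activity and the baseline value of the measure.
- Project SAP 4.4.2.3.1 analyses UC-PRO/SS by an MMRM with "fixed categorical effects of treatment, visit, study stratification factors, and treatment-by-visit interaction". Project SAP 4.4.2.3 says of the UC-PRO that "two domains are key endpoints and reported as UC-PRO Signs and Symptoms".
- Project SAP 4.4.2.4 analyses IBDQ by ANCOVA with the factors used at randomisation. Study SAP 4.4.2.12 places IBDQ outside the multiple testing procedure.
- Study SAP 4.4.3 gives the exploratory continuous endpoints the same methods. Study SAP 4.4.5 lists a supplementary logistic model without naming its covariates.

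**The concern.** A technical claim about one test is used to set the covariates of every Maintenance model. If the claim is wrong, the removal has no stated reason. Even if it were right, it would say nothing about an ANCOVA, MMRM or logistic model, where the factor enters as a main effect and empty cross-classified cells do no harm.

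The practical result falls on the continuous endpoints. The protocol names Week 10 remission in their model and the study SAP takes it out. Study SAP 3.1.1 states the removal openly but does not identify it as a departure from Protocol 6.4.2. The project SAP still points to the randomisation factors for IBDQ, so whoever programs that analysis has conflicting instructions. At stake is precision: leaving out a prognostic factor that was balanced by design makes the reported standard error too large.

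**Working it through.** **The plan's own figure.** Inputs from Protocol 6.1: 105 per arm, placebo 30%, difference 25 points, two-sided 5%. The mean rate is 0.425.

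- Null SE = sqrt(2 x 0.425 x 0.575 / 105) = 0.0682
- Alternative SE = sqrt((0.30 x 0.70 + 0.55 x 0.45) / 105) = 0.0660
- z = (0.25 - 1.96 x 0.0682) / 0.0660 = 1.76, so power is 96.1%

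At placebo 35% or 40% power is 95.8%, and at 45% it is 96.1%. The stated figure of more than 90% is reproduced.

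**Does a sparse stratum invalidate the CMH test?** Four factors give 2 x 2 x 2 x 3 = 24 strata, or 210/24 = 8.75 patients each on average, so sparsity is to be expected. For a stratum with n1 and n0 patients per arm, m events and N = n1 + n0, let a be the events in the first arm. The stratum adds a - E to the numerator, with E = n1 m / N, and V = n1 n0 m (N - m) / [N² (N - 1)] to the variance.

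- n1 = 0: a = E = 0 and V = 0.
- n0 = 0: a = E = m and V = 0.
- m = 0: a = E = 0 and V = 0.
- m = N: a = E = n1 and V = 0.

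Such a stratum carries no information. It does not bias or break the test.

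**Simulation of the CMH test.** N = 210, 10,000 null trials in each of nine scenarios. Assumed, because the documents do not give them: permuted blocks of 4, corticosteroids 45%, immunosuppressants 30%, MCS of 10 or more in 40%, Week 10 remitters 20 to 45%, odds ratio of Week 10 remission for the Week 62 outcome 1, 2 or 4.

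| | 24 strata (factor kept) | 8 strata (factor dropped) |
|---|---|---|
| Type I error | 4.7 to 5.3% | 4.0 to 5.2% |
| Power at an assumed 20-point effect | 83 to 87% | 83 to 85% |

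On average 9 to 13 of the 24 strata held fewer than 5 patients. The Mantel-Fleiss quantity never fell below 13 (the usual rule asks for at least 5).

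**Main-effect models.** The three-level factor costs 2 degrees of freedom. If it explains a share R² of residual variance, restoring it multiplies the ANCOVA standard error by about sqrt(1 - R²): 0.990 at 2%, 0.975 at 5%, 0.949 at 10%. Under perfect balance the model without the factor in effect tests at 1.96 / sqrt(1 - R²). That is 2.01 at 5% (true level about 4.4%) and 2.07 at 10% (about 3.9%), so the test is conservative.

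Simulated ANCOVA: n = 210, remitters 10 to 45%, MCS of 10 or more in 45%, assumed effect 0.35 SD, the two remission levels merged when one held fewer than 5 patients.

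| Variance explained (assumed) | SE change on restoring | Type I error without it | Power change, points (71 to 73% without it) |
|---|---|---|---|
| 0% | +0.1 to +0.2% | 4.8 to 5.3% | -0.2 to 0.0 |
| 2% | -0.8 to -0.9% | 4.9 to 5.1% | +0.6 to +0.9 |
| 5% | -2.3 to -2.4% | 4.5 to 4.9% | +1.7 to +1.9 |
| 10% | -5.0 to -5.1% | 3.9 to 4.3% | +3.0 to +3.9 |

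With the factor restored, type I error was 4.7 to 5.4% throughout.

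For scale, treat remission as yes/no with remitter share f. The shift d between remitters and non-remitters, in residual SD, satisfies d² = R² / [(1 - R²) f (1 - f)]. At f = 20%, R² of 5% means d = sqrt(0.0526 / 0.16) = 0.57. At f = 10%, R² of 10% means d = sqrt(0.111 / 0.09) = 1.1, which is a strong effect.

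**The case against.** **What stands.** The primary analysis loses nothing relative to the protocol. A reader might infer that a protocol factor was taken out of the primary test or that type I error is at risk. Protocol 6.4.1 lists the same three factors, and the error moves, if at all, below 5%. The review behind the removal was blinded, and the sparsity it expects is real.

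A reader might also infer that this is the one departure the SAP left unmarked, since it does mark others: "The efficacy outcome measures listed below deviate from the current Study GA29102 Protocol Version 7" in 2.2 and "This differs to terminology in the Protocol Version 7, Section 6.4, which uses intent-to-treat population" in 4.1.2.1. The documents do not support that contrast. Truncated Holm gatekeeping replaces the protocol's sequential 5% tests, and the MMRM replaces its ANCOVA for UC-PRO/SS, and neither is marked as a departure from the protocol. Because of that change, IBDQ is the secondary endpoint still under the protocol's ANCOVA, and it is outside multiplicity control.

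Study SAP 3.1 says that "further combining or removal may be required to ensure the analysis is not invalidated due to zero counts". One could read this as a licence to strip factors from any model. The clause sits in text about the CMH test in the primary analysis, so that reading goes too far.

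The gain is modest, and for the MMRM it was not computed. UC-PRO/SS is also collected at Weeks 4, 8 and 10, and the SAP does not say which visits enter the model. If Week 10 enters, part of the remission information may already be carried.

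**What does not stand.** Some stratified confidence interval methods do fail with one-arm strata, and the documents do not state the method for the risk difference. The SAP may have had the interval in mind. That could support a three-factor CMH analysis, which the protocol specifies anyway. It gives no reason to change the ANCOVA or MMRM.

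**Conclusion.** The point holds for the stated rationale and for the continuous endpoints. The sentence in study SAP 3.1.1 about the CMH test is incorrect, and it is applied to models it does not concern. For the continuous secondary endpoints it contradicts Protocol 6.4.2, and for IBDQ also project SAP 4.4.2.4. The three-factor CMH for the primary and responder endpoints is valid and should stay.

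The consequence is a slightly conservative, less efficient comparison. The ANCOVA standard error is unnecessarily large by roughly 0 to 5% if Week 10 remission explains 0 to 10% of residual variance. That range is an assumption, because the documents give no prognostic strength. This is worth correcting, but it does not threaten the trial's main conclusion.

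**What to change.** 1. Correct the rationale in study SAP 3.1.1: sparse strata contribute little or nothing to the CMH statistic but do not invalidate it. Limit the removal to the CMH analyses and cite Protocol 6.4.1 as its basis.
2. Restore Week 10 remission as a main effect in the IBDQ ANCOVA, the UC-PRO/SS MMRM, the exploratory continuous models and any logistic model adjusted for the randomisation factors. Use the three randomised levels, and merge the two remission levels if one is too sparse on pooled blinded counts.
3. Reconcile Protocol 6.4.2, study SAP 3.1.1 and project SAP 4.4.2.4, and name any departure that remains.

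Optional: a sensitivity CMH that also stratifies by Week 10 remission (none versus any, 16 strata). With few remitters and no prognostic effect it could lose up to 1.2 power points at an assumed 15-point effect, so it should not replace the primary.

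The cost is SAP wording and programming, since the factor is already held in IxRS. If the factor proves not to be prognostic, the simulated ANCOVA loses at most 0.2% in standard error and 0.2 power points.
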